8.3.2 Direct access to source data and documents

The sponsor will monitor the conduct of the trial by regular on-site monitoring visits and inhouse data quality review. The frequency of on-site monitoring will be determined by assessing all characteristics of the trial, including its nature, objective, methodology and the degree of any deviations of the intervention from normal clinical practice.

The Investigator /institution will allow on-site trial-related monitoring, audits, IRB / IEC review and regulatory inspections. Direct access must be provided to the eCRF and all source documents/data, including progress notes, copies of laboratory and medical test results, which must be available at all times for review by the CRA, auditor and regulatory inspector (e.g. FDA). The CRA and auditor may review all eCRFs and informed consents. The accuracy of the data will be verified by direct comparison with the source documents described in section 8.3.1. The sponsor will also monitor compliance with the protocol and ICH GCP.

8.3.3 **Storage period of records**

Trial site(s):

The trial site(s) must retain the source and essential documents (including ISF) according to the national or local requirements (whatever is longer) valid at the time of the end of the trial.

Sponsor:

The sponsor must retain the essential documents according to the sponsor's SOPs.

8.4 EXPEDITED REPORTING OF ADVERSE EVENTS

BI is responsible to fulfil their legal regulatory reporting obligation and in accordance to the requirements defined in this CTP.

8.5 STATEMENT OF CONFIDENTIALITY AND PATIENT PRIVACY

Individual patient data obtained as a result of this trial is considered confidential and disclosure to third parties is prohibited with the exceptions noted below. Patient privacy will be ensured by using patient identification code numbers.

Data protection and data security measures are implemented for the collection, storage and processing of patient data in accordance with the principles 6 and 12 of the WHO GCP handbook.

Treatment data may be given to the patient's personal physician or to other appropriate medical personnel responsible for the patient's welfare. Data generated as a result of the trial need to be available for inspection on request by the participating physicians, the sponsor's representatives, by the IRB / IEC and the regulatory authorities.

8.5.1 Collection, storage and future use of biological samples and corresponding data

Measures are in place to comply with the applicable rules for the collection, storage and future use of biological samples from clinical trial participants and the corresponding data, in particular

- A Quality Management System has been implemented to ensure the adherence with the Principles of Good Clinical Practice as outlined in 'Note For Guidance On Good Clinical Practice' (CPMP/ICH/13 5/95)
- The BI-internal facilities storing and analysing biological samples and data from clinical trial participants as well as the laboratories' activities for clinical trials sponsored by Boehringer Ingelheim are regularly audited. The analytical groups and the banking facility are therefore assessed to be qualified for the storage and use of biological samples and data collected in clinical trials.
- Samples and data are used only if an appropriate informed consent is available.

8.6 TRIAL MILESTONES

The **start of the trial** is defined as the date of the enrolment of the first patient in the whole trial. **The end of the trial** is defined as the date of the last visit of the last patient in the whole trial ("Last Patient Out"). The "**Last Patient Drug Discontinuation**" (LPDD) date is defined as the date on which the last patient at an individual trial site ends trial medication (as scheduled per protocol or prematurely). Individual Investigators will be notified of Suspected Unexpected Serious Adverse Reactions (SUSARs) occurring with the trial medication until 30 days after LPDD at their site.

Early termination of the trial is defined as the premature termination of the trial due to any reason before the end of the trial as specified in this protocol.

Temporary halt of the trial is defined as any unplanned interruption of the trial by the sponsor with the intention to resume it.

Boehringer Ingelheim		4 February 2016
BI Trial No.: 1321.7		
c08884404-01	Trial Protocol	Page 63 of 77
Proprietary confidential information © 2	016 Boehringer Ingelheim International GmbH or one	or more of its affiliated companies

Suspension of the trial is defined as an interruption of the trial based on a Health Authority request. The IEC / competent authority in each participating EU member state will be notified about the trial milestones according to the respective laws.

A final report of the clinical trial data will be written only after all patients have completed the trial in all countries (EU or non-EU) to incorporate and consider all data in the report. The sponsor will submit to the EU database a summary of the final trial results within one year from the end of a clinical trial as a whole, regardless of the country of the last patient (EU or non-EU).

Page 64 of 77

Proprietary confidential information © 2016 Boehringer Ingelheim International GmbH or one or more of its affiliated companies

9 **REFERENCES**

10 APPENDICES

10.1 SAFETY AND OTHER CLINICAL LABORATORY EVALUATIONS

Standard safety lab panel may include when feasible parameters as described in section 5.3.3.

Estimated Glomerular Filtration Rate (eGFR) for children should be based on the Schwartz formula. This employs serum creatinine (mg/dL), the child's height (cm) and a constant to estimate the glomerular filtration rate:

eGFR (Schwartz) = (0.41 x Height in cm) / Serum Creatinine in mg/dL

Conversion from conventional unit to SI unit:

Conventional unitConversion FactorSI Unitmg/mL88.4µmol/L

10.2 TIME SCHEDULE FOR BLOOD SAMPLING

Blood volumes to be collected for central lab parameters and local safety lab measurements will depend on available tube sizes and age of the patient as specified in Table 10.2: 1 and Table 10.2: 2. The sponsor may decide on other tubes sizes, if necessary. In such case total blood volume of the blood sampling may differ.

Cross reporting of lab results might be applied (across studies 1160.106, 1160.108 and this trial) in order not to increase the blood volume required for analysis.

Pre-dose and between vials sampling: central blood sampling for pharmacodynamic biomarkers (dTT, ECT, aPTT, TT), pharmacokinetics (dabigatran and idarucizumab concentration) will occur immediately prior to administration of each vial of idarucizumab. Blood sampling for idarucizumab ADA will only occur prior to vial 1 administration.

Post-dose sampling: central blood sampling for pharmacodynamic biomarkers (dTT, ECT, aPTT, TT), pharmacokinetics (dabigatran and idarucizumab concentrations) will be collected at 30 minutes (\pm 10 minutes), 4 hours (\pm 30 minutes), 12 hours (\pm 1 hour) and 24 hours (\pm 2 hours) post-dose. Blood sampling for idarucizumab ADA will occur 30 days (+7 days) post-dose.

In Table 10.2.: 1, general required blood volumes are indicated for age category < 6 years of age. For children < 6 years of age, available tube sizes for central lab parameters are 1.2 mL, and 2.7 mL EDTA monovettes and 1.4 mL Na Citrate monovettes. For all central lab parameters and local safety lab measurements about 29 to 37 mL blood will be required during the trial.

In Table 10.2.: 2, general required blood volumes are indicated for age category ≥ 6 years of age. For children ≥ 6 years of age, available tube sizes for central lab parameters are 3.0 mL

Boehringer Ingelheim		4 February 2016
BI Trial No.: 1321.7		
c08884404-01	Trial Protocol	Page 69 of 77
Proprietary confidential information ©	2016 Boehringer Ingelheim International GmbH or one of	or more of its affiliated companies

EDTA vacutainers and 2.7 mL Na Citrate vacutainers. For all central lab parameters and local

EDTA vacutainers and 2.7 mL Na Citrate vacutainers. For all central lab parameters and local safety lab measurements about 43 to 49 mL blood will be required during the trial.

All efforts should be made to use the lowest amount of blood per sample as technically possible by using special paediatric collection systems (R10-4556; R10-4959). Blood sampling for this trial and for dabigatran trial 1160.106 or 1160.108 should not exceed the maximum blood volume limits recommended by the European Commission (R10-4959) nor the maximum specified in local guidelines (if applicable), i.e. blood loss should not exceed 3% of the total blood volume (TBV) over four weeks and should not exceed 1% of the TBV at any single time.

Blood sampling could be withheld or reduced per Investigator's judgement, e.g. if limited by blood volume, bleeding and/or distress considerations especially in very young children. Refer to appendix 10.3 for several reduced blood draw schedules.

All invasive procedures in this trial must be performed only by qualified and experienced health care professionals/physicians with paediatric expertise, with limited attempts to draw blood and/or establish an intravenous (IV) line based on Investigator's judgement. Prior to venipuncture, a topical (percutaneous) analgesia to reduce pain associated with venipuncture, e.g. amethocaine gel or lidocaine-prilocaine (Emla) cream should be applied on the skin. This should be done according to standard paediatric procedures, and may be omitted only in patients who explicitly refuse it.

Boehringer Ingelheim BI Trial No.: 1321.7 c08884404-01

Trial Protocol

Page 70 of 77

Proprietary confidential information © 2016 Boehringer Ingelheim International GmbH or one or more of its affiliated companies

Table 10.2: 1

Blood draw schedule (patients < 6 years of age)

		Time	EDTA*	Na Citrate**	Local Safety Lab***	Total blood volume
Visit 1	1	Screening	/////	//////	$\sim 2 \text{ to } 6 \text{ mL}$	~ 2 to 6 mL
Visit 2.1	2	Baseline (just prior vial 1)	2.7 mL	1.4 mL		4.1 mL
		Adminis	ster Idaruciz	zumab Vial	1	
Visit 2.2	3	Just prior vial 2	2.7 mL	1.4 mL		4.1 mL
		Adminis	ster Idaruciz	zumab Vial 2	2	
Visit 2.2	4	30 minutes (± 10 minutes)	2.7 mL	1.4 mL		4.1 mL
	5	4 hours (± 30 minutes)	2.7 mL	1.4 mL		4.1 mL
	6	12 hours $(\pm 1 \text{ hour})$	2.7 mL	1.4 mL		4.1 mL
Visit 3	7	24 hours (± 2 hours)	2.7 mL	1.4 mL	~ 2 to 6 mL	~ 6 to 10 mL
Visit 4	8	Day 7 (± 3 days)				
Visit 5	9	Day 30 (+ 7 days)	1.2 mL	()))))		1.2 mL
Total blood	volur	ne				~29 to 37 mL

*EDTA K3 = PK assays, idarucizumab ADA

**Na Citrate = Biomarkers (dTT, ECT, aPTT, TT)

***Amount of mL will depend on tube sizes used by local lab.

Boehringer Ingelheim BI Trial No.: 1321.7 c08884404-01

4 February 2016

Trial Protocol

Page 71 of 77

Proprietary confidential information © 2016 Boehringer Ingelheim International GmbH or one or more of its affiliated companies

Table 10.2: 2

Blood draw schedule (patients ≥ 6 years of age)

		Time	EDTA*	Na Citrate**	Local Safety Lab***	Total blood volume
Visit 1	1	Screening			~ 3 to 6 mL	~ 3 to 6 mL
Visit 2.1	2	Baseline (just prior vial 1)	3.0 mL	2.7 mL		5.7 mL
		Admini	ster Idarucia	zumab Vial 1	l	
Visit 2.2	3	Just prior vial 2	3.0 mL	2.7 mL		5.7 mL
		Admini	ster Idaruciz	zumab Vial 2	2	
Visit 2.2	4	30 minutes $(\pm 10 \text{ minutes})$	3.0 mL	2.7 mL		5.7 mL
	5	4 hours $(\pm 30 \text{ minutes})$	3.0 mL	2.7 mL		5.7 mL
	6	12 hours (± 1 hour)	3.0 mL	2.7 mL		5.7 mL
Visit 3	7	24 hours (± 2 hours)	3.0 mL	2.7 mL	~ 3 to 6 mL	~ 9 to 12 mL
Visit 4	8	Day 7 (± 3 days)				
Visit 5	9	Day 30 (+ 7 days)	3.0 mL			3.0 mL
Total blood v	volun	ne				~43 to 49 mL

*EDTA = PK assays, idarucizumab ADA

**Na Citrate = Biomarkers (dTT, ECT, aPTT, TT)

***Amount of mL will depend on tube sizes used by local lab.

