Pre-dose and between vials sampling: central blood sampling for pharmacodynamic biomarkers (dTT, ECT, aPTT, TT), pharmacokinetics (dabigatran and idarucizumab concentration) will occur immediately prior to administration of each vial of idarucizumab. Blood sampling for idarucizumab ADA will only occur prior to vial 1 administration.

Post-dose sampling: central blood sampling for pharmacodynamic biomarkers (dTT, ECT, aPTT, TT), pharmacokinetics (dabigatran and idarucizumab concentrations) will be collected at 30 minutes (\pm 10 minutes), 4 hours (\pm 30 minutes), 12 hours (\pm 1 hour) and 24 hours (\pm 2 hours) post-dose. Blood sampling for idarucizumab ADA will occur 30 days (+7 days) post-dose.

Blood sampling could be withheld or reduced per Investigator's judgement, e.g. if limited by blood volume, bleeding and/or distress considerations especially in very young children. E.g. omission of exploratory coagulation markers, reduced frequency of safety labs during the treatment period, etc.

Refer to appendix 10.3 for detailed information (priority order of lab parameters). The decision for reduced blood collection in those cases will be documented in the medical notes and CRF.

Time will be recorded for every blood sample taken.

Boehringer Ingelheim		4 February 2016
BI Trial No.: 1321.7		
c08884404-01	Trial Protocol	Page 7 of 77

⁸ Includes Haematology and Chemistry. Optional local blood draws for aPTT and other local lab testing may be done at the discretion of the treating physician to facilitate patient clinical management.

⁹ Local urine or other appropriate spot pregnancy test in female adolescents of child bearing potential (patients who have reached menarche). More frequent testing can be done if required by the local regulation and/or authority or per Investigator's judgement. Enrolment of pregnant patients is not allowed.

¹⁰ Re-start of anticoagulant therapy, if applicable, can be a return to dabigatran etexilate for patients from Group B. Patients from Group A have to be switched to a standard of care anticoagulant medication.

¹¹ Also needs to be completed if the patient withdraws prematurely following first vial of trial medication or at any later time point prior end of trial.

08884404-01Trial ProtocolPage 8 of 77Proprietary confidential information © 2016 Boehringer Ingelheim International GmbH or one or more of its affiliated companies

TABLE OF CONTENTS

TITLE PA	GE	1
CLINICA	L TRIAL PROTOCOL SYNOPSIS	2

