3.3.3 Exclusion criteria

Group A:

- 1. Patients with minor bleeding (e.g. epistaxis, haematuria) who can be managed with standard supportive care.
- 2. Patients with no clinical signs of bleeding.
- 3. Patients with body weight < 2.5 kg
- 4. Contraindications to trial medication including known hypersensitivity to the drug or its excipients; e.g. patients with known hereditary fructose intolerance who may react to sorbitol.
- 5. Female patients who are pregnant, nursing, or who plan to become pregnant while in the trial.

Group B:

- 1. A surgery or procedure which is elective or where the risk of uncontrolled or unmanageable bleeding is low.
- 2. Patients with body weight < 2.5 kg
- 3. Contraindications to trial medication including known hypersensitivity to the drug or its excipients; e.g. patients with known hereditary fructose intolerance who may react to sorbitol.
- 4. Female patients who are pregnant, nursing, or who plan to become pregnant while in the trial.

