10.3 ESTIMATED TOTAL BLOOD VOLUME

The estimated Total Blood Volume (TBV) will depend on age and gender and will be calculated with following formula:

Total Blood Volume = Weight * Average Blood Volume

Table 10.3.1:Approximate (average) blood volume per age category.

Age category	Approximate (average) blood volume (mL/Kg)
Term newborn infant	80 - 90 (85)
Infants	80
Children (> 3 months)	70-80
Adolescents	
women	65
men	75

For children the approximate total blood volume may vary between 70 - 80 mL/Kg. In order to be conservative, 70 mL/Kg will be used to calculate the total blood volume (TBV).

Examples of TBV calculations:

Infant of 1.5 year old, weight 10 Kg:

- Allowed blood loss at any single time (1% of TBV): 8 mL
- Allowed blood loss over four weeks (3% of TBV): 24 mL

Child of 12 years old, weight 45 Kg:

- Allowed blood loss at any single time (1% of TBV): 31.5 mL
- Allowed blood loss over four weeks (3% of TBV): 94.5 mL

Adolescent (male) of 15 years old, weight 60 Kg:

- Allowed blood loss at any single time (1% of TBV): 45 mL
- Allowed blood loss over four weeks (3% of TBV): 135 mL

Blood sampling could be withheld or reduced per Investigator's judgement, e.g. if limited by blood volume, bleeding and/or distress considerations especially in very young children.

If blood sampling is reduced, central lab parameters will be analysed in a priority order as indicated below:

- 1) Sum dabigatran pre-dose (baseline)
- 2) All coagulation biomarkers pre-dose, 30 minutes and 24 hours post-dose
- 3) Idarucizumab ADA pre-dose and 30 days post-dose
- 4) PK idarucizumab at time points pre-dose; 30 minutes and 24 hours post-dose
- 5) All coagulation biomarkers at time points prior vial 2, 4 hours and 12 hours post-dose
- 6) PK idarucizumab at time points prior vial 2, 4 hours and 12 hours post-dose

Boehringer Ingelhein	1	4 February 2016
BI Trial No.: 1321.7		
c08884404-01	Trial Protocol	Page 73 of 77
D		0.1. 0011 1

7) Unbound sum dabigatran at all time points as noted in Flow Chart

In below tables a few scenarios are displayed if collected blood volumes are limited.

Table 10.3: 1Reduced blood draw schedule (patients < 6 years of age):
Maximal 29 mL central lab/local safety blood draw (e.g. no EDTA blood
collection prior vial 2, 4 hours and 12 hours post-dose; i.e. no measurement of
unbound sum dabigatran and no PK idarucizumab prior vial 2, 4 hours and 12
hours post-dose)

		Time	EDTA	Na Citrate	Local Safety Lab	Total blood volume

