Visit 1	1	Screening	11111		$\sim 2 \text{ to } 6 \text{ mL}$	~ 2 to 6 mL
Visit 2.1	2	Baseline (just prior vial 1)	2.7 mL	1.4 mL		4.1 mL
		Admini	ster Idaruciz	zumab Vial	1	
Visit 2.2	3	Just prior vial 2		1.4 mL		1.4 mL
	•	Admini	ster Idaruciz	zumab Vial	2	
Visit 2.2	4	30 minutes $(\pm 10 \text{ minutes})$	2.7 mL	1.4 mL		4.1 mL
	5	4 hours (± 30 minutes)		1.4 mL		1.4 mL
	6	12 hours (± 1 hour)		1.4 mL		1.4 mL
Visit 3	7	$\begin{array}{c} 24 \text{ hours} \\ (\pm 2 \text{ hours}) \end{array}$	2.7 mL	1.4 mL	~ 2 to 6 mL	~ 6 to 10 mL
Visit 4	8	Day 7 (± 3 days)				
Visit 5	9	Day 30 (+ 7 days)	1.2 mL			1.2 mL
Total blood	Total blood volume					~21 to 29 mL

Boehringer Ingelheim		4 February 2016
BI Trial No.: 1321.7		
c08884404-01	Trial Protocol	Page 74 of 77
		C' CC'1' 1 '

Table 10.3: 2Reduced blood draw schedule (patients < 6 years of age):	Maximal **25 mL** central lab/local safety blood draw (e.g. no blood collection prior vial 2, 4 hours and 12 hours post-dose; i.e. no measurement of biomarkers, unbound sum dabigatran and no PK idarucizumab prior vial 2, 4 hours and 12 hours post-dose)

		Time	EDTA	Na Citrate	Local Safety Lab	Total blood volume
Visit 1	1	Screening			~ 2 to 6 mL	~ 2 to 6 mL
Visit 2.1	2	Baseline (just prior vial 1)	2.7 mL	1.4 mL		4.1 mL
		Admini	ster Idaruciz	zumab Vial	1	
Visit 2.2	3	Just prior vial 2				
		Admini	ster Idaruciz	zumab Vial	2	
Visit 2.2	4	30 minutes (± 10 minutes)	2.7 mL	1.4 mL		4.1 mL
	5	4 hours (± 30 minutes)				
	6	12 hours $(\pm 1 \text{ hour})$				
Visit 3	7	$\begin{array}{c} 24 \text{ hours} \\ (\pm 2 \text{ hours}) \end{array}$	2.7 mL	1.4 mL	~ 2 to 6 mL	~ 6 to 10 mL
Visit 4	8	Day 7 (± 3 days)				
Visit 5	9	Day 30 (+ 7 days)	1.2 mL			1.2 mL
Total blood volume					~17 to 25 mL	

Boehringer Ingelheim		4 February 2016
BI Trial No.: 1321.7		
c08884404-01	Trial Protocol	Page 75 of 77
		C'1 CC1' 1 1

Table 10.3: 3 Reduced blood draw schedule (patients \geq 6 years of age):

Maximal **40 mL** central lab/local safety blood draw (e.g. no EDTA blood collection prior vial 2, 4 hours and 12 hours post-dose; i.e. no measurement of unbound sum dabigatran and no PK idarucizumab prior vial 2, 4 hours and 12 hours post-dose)

		Time	EDTA	Na Citrate	Local Safety Lab	Total blood volume
Visit 1	1	Screening			~ 3 to 6 mL	~ 3 to 6 mL
Visit 2.1	2	Baseline (just prior vial 1)	3.0 mL	2.7 mL		5.7 mL
		Admini	ster Idaruciz	umab Vial 1	l	
Visit 2.2	3	Just prior vial 2		2.7 mL		2.7 mL
		Admini	ster Idaruciz	zumab Vial 2	2	

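### For children of 2.5 to 5.499 kg, no printed blood-draw schedule meets the protocol's own 3% four-week limit once its local safety labs are counted

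*Protocol*

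**What the plan says.** Protocol sections 5.3.3 and 10.2 set two ceilings: "blood loss should not exceed 3% of the total blood volume (TBV) over four weeks", and a draw "should not exceed 1% of the TBV at any single time". Both apply to this trial and trial 1160.106 or 1160.108 taken together. Appendix 10.3 gives the formula "Total Blood Volume = Weight * Average Blood Volume". Its Table 10.3.1 lists 80 to 90 mL/kg for term newborns (average 85), 80 for infants and 70 to 80 for children over 3 months, with 70 as the conservative choice for children.

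The smallest patients are eligible. Section 3.3.3 excludes only "Patients with body weight < 2.5 kg", and Table 4.1.2: 1 has a 2.5 to 5 kg dose band, which reaches 5.499 kg under the rounding rule in section 4.1.2.

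For children under 6 years, section 10.2 describes the full schedule thus: "For all central lab parameters and local safety lab measurements about 29 to 37 mL blood will be required during the trial". It then refers sites to appendix 10.3 for reduced schedules. The smallest of these, Table 10.3: 2, is labelled as a maximal 25 mL "central lab/local safety blood draw (e.g. no blood collection" before vial 2 and at 4 and 12 hours. Its printed total is about 17 to 25 mL.

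The appendix also lets the investigator reduce sampling, ranks the central laboratory parameters in seven steps, and presents the reduced tables as examples. Section 10.2 allows the sponsor to choose other tube sizes and allows laboratory results to be shared across the three trials.

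**The concern.** The limits and the schedules stand in the same appendices, and a site will naturally take a reduced table from appendix 10.3 as a way to stay within the limits. In the lowest weight band it is not one: a site that follows the smallest table as printed exceeds the protocol's ceiling in an infant who may already be bleeding.

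A site that keeps to the ceiling must work out, in an emergency, which tubes to leave out. The ranking helps with the central tests but carries no volumes and says nothing about the local safety labs. The only scheduled post-dose local safety lab is the one at 24 hours, and safety is the primary endpoint. With about five patients and no imputation of missing values (Protocol 7.5, SAP 6.6), data lost in one infant cannot be recovered.

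**Working it through.** **1. Reproduce the printed totals (children under 6 years).** A central draw is 2.7 mL EDTA + 1.4 mL citrate = 4.1 mL. The Day 30 tube is 1.2 mL. Two local safety draws take 2 to 6 mL each.

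- Table 10.2: 1: 6 × 4.1 + 1.2 + 2 × (2 to 6) = 29.8 to 37.8 mL (printed about 29 to 37).
- Table 10.3: 1: 3 × 4.1 + 3 × 1.4 + 1.2 + 2 × (2 to 6) = 21.7 to 29.7 mL (printed about 21 to 29).
- Table 10.3: 2: 3 × 4.1 + 1.2 + 2 × (2 to 6) = 17.5 to 25.5 mL (printed about 17 to 25).

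The protocol's example of a 10 kg infant also reproduces: 10 × 80 = 800 mL, so 1% is 8 mL and 3% is 24 mL.

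**2. Volume within four weeks.** The Day 30 window runs only forward (+7 days), so that tube falls outside four weeks from dosing. Table 10.3: 2 then takes 17.5 − 1.2 = 16.3 mL to 25.5 − 1.2 = 24.3 mL.

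**3. Compare with 3%.** Limit = 0.03 × weight × mL/kg. A volume V fits from weight V / (0.03 × mL/kg). The last two columns are the lowest weights at which 16.3 mL (both local labs at 2 mL) and 12.3 mL (no local labs) fit.

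| mL/kg | Limit at 2.5 kg (mL) | Limit at 5.499 kg (mL) | 16.3 mL as a multiple of the limit, from 2.5 to 5.499 kg | 16.3 mL fits from | 12.3 mL fits from |
|---|---|---|---|---|---|
| 70 | 5.25 | 11.55 | 3.1 to 1.4 | 7.8 kg | 5.9 kg |
| 80 | 6.00 | 13.20 | 2.7 to 1.2 | 6.8 kg | 5.1 kg |
| 85 | 6.38 | 14.02 | 2.6 to 1.2 | 6.4 kg | 4.8 kg |
| 90 | 6.75 | 14.85 | 2.4 to 1.1 | 6.0 kg | 4.6 kg |

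With both local labs counted, 16.3 mL is over the limit throughout 2.5 to 5.499 kg at every factor. At the upper volume, 24.3 mL fits only from 9.5 kg (85 mL/kg) to 11.6 kg (70). At the protocol's own 10 kg example it takes 24.3 mL against 24 mL allowed.

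**4. Take out local labs.** Without the screening lab the volume is 16.3 − 2 = 14.3 mL. That exceeds 14.02 mL, so the whole band is still over at 85 mL/kg; at 90 it fits from 14.3 / 2.7 = 5.3 kg. Without either local lab, 3 × 4.1 = 12.3 mL remains, which exceeds 3% below 12.3 / 2.55 = 4.8 kg at 85 mL/kg.

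**5. Compare single draws with 1%.** At 85 mL/kg the 4.1 mL central draw exceeds 1% below 4.1 / 0.85 = 4.8 kg. The 24-hour draw, at least 4.1 + 2 = 6.1 mL, exceeds it below 6.1 / 0.85 = 7.2 kg.

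**6. Not counted.** Blood taken for the parent trial in the same four weeks shares these limits. The documents give no volume for it, so these results understate the excess.

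**The case against.** The strongest reply is that the limits govern and the tables do not. The reduced tables are offered as examples, Table 10.3: 2 is labelled as a maximum, and the protocol foresees small children: the investigator may cut sampling because of blood volume, volumes are to be kept as low as technically possible, central tests are ranked, the sponsor may change tubes, and results may be shared between trials. Screening tests already done in routine care are not to be repeated. Exposure is also small: about five patients, the first expected at 12 to 18 years (Protocol 3.2).

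Much of this stands, and it rules out four stronger readings.

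- A reader might infer that a site has no compliant course and is left to improvise. It may reduce sampling, and the seven-step order guides the central tests.
- A reader might infer that every child in the band is over the limit whatever is counted. That needs the local labs in the count; without them 12.3 mL fits from about 4.8 kg at 85 mL/kg.
- Flow Chart footnote 7 gives "reduced frequency of safety labs during the treatment period, etc" as an example of reduction, which might be read as an invitation to drop the 24-hour safety lab. That lab belongs to Visit 3, in the Safety Follow-Up Period, so the example does not name it.
- A reader might fear that the pre-dose sample is at risk. Pre-dose sum dabigatran and the pre-dose biomarkers are in the first two steps of the order, so they are the best protected.

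The reply does not reconcile the tables with the limits. The order gives no volumes and leaves out the local labs. Tube size is the sponsor's decision, not one a site can make at the bedside. Sharing results is optional, and nothing shows that parent-trial samples would coincide with the timed post-dose draws.

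**Conclusion.** The point holds as an inconsistency between the printed schedules and the printed limits. Counting local safety labs, no schedule in appendix 10.2 or 10.3 meets 3% of total blood volume for a child of 2.5 to 5.499 kg, at any blood volume per kg that the protocol lists. Part of the 6 to 10 kg band is affected too. Without local labs the excess remains at the lower weights, and the 1% ceiling is broken by individual draws as well.

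The size rests on three assumptions: local draws at their printed minimum of 2 mL, four weeks counted from dosing, and no parent-trial blood. The first and third favour the plan; the second excludes the Day 30 tube. The protocol does not force a breach. It leaves the site to derive a compliant schedule from a ranking without volumes. Because few infants are expected, this should be corrected but does not threaten the trial as a whole.

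**What to change.** Reconcile the tables in appendices 10.2 and 10.3 with the 1% and 3% limits:

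- State under each table the lowest weight at which it complies, and with which local labs counted.
- Print both limits in mL by kg, from 2.5 kg upward, and note that parent-trial blood is to be deducted.
- Add a reduced schedule for the lowest weights that follows the existing priority order. The sponsor should confirm its tube volumes against assay needs, which the documents do not give, and check it against both limits down to 2.5 kg. Small tubes alone do not settle this: the smallest listed pair for this age group, 1.2 mL EDTA with 1.4 mL citrate, makes 2.6 mL and exceeds 1% below 2.6 / 0.85 = 3.1 kg.
- Give the 24-hour local safety lab an explicit place in the order.

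The cost is a small appendix change and a check with the laboratories. The smallest infants will contribute fewer PK and intermediate biomarker values, which the limits already preclude.
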